6.2.1. Week 1 (\pm 3 days)

The following procedures/assessments are to be completed at the end of Week 1:

- Obtain vital signs (refer to Section 6.7.4)
- Assessment of AEs and concomitant medications
- Assess adherence with study drug dosing regimen including pill count

6.2.2. Week 2 (\pm 3 days)

The following procedures/assessments are to be completed at the end of Week 2:

- Obtain vital signs (refer to Section 6.7.4)
- Assessment of AEs and concomitant medications
- Assess adherence with study drug dosing regimen including pill count
- Obtain blood samples for tests:
 - Hematology
 - Chemistry
 - HCV RNA
 - HCV resistance samples
 - HBV DNA Sample

6.2.3. Weeks 4 and 8 (\pm 3 days)

The following procedures/assessments are to be completed at the end of Weeks 4 and 8:

- Obtain vital signs (refer to Section 6.7.4)
- Assessment of AEs and concomitant medications
- Assess adherence with study drug dosing regimen including pill count
- Dispense study drug as directed by the IWRS (Week 4 only)
- Obtain blood samples for tests:
 - Hematology
 - Chemistry
 - HCV RNA
 - HCV resistance samples
 - HBV DNA Sample
- Obtain urine sample for:
 - Pregnancy test for females of childbearing potential only

6.2.4. Week 12 (\pm 3 days)

The following procedures/assessments are to be completed at the end of Week 12:

- Perform complete physical examination (refer to Section 6.7.3)
- Obtain weight
- Obtain vital signs (refer to Section 6.7.4)
- Assessment of AEs and concomitant medications
- Perform 12-Lead ECG (refer to Section 6.7.5)
- Conduct pregnancy prevention counseling
- Assess adherence with study drug dosing regimen including pill count
- Collect any remaining study drug from the subject

- Obtain blood samples for tests:
 - Hematology
 - Chemistry
 - Coagulation tests
 - HCV RNA
 - HCV resistance samples
 - HBV DNA Sample
- Obtain urine sample for:
 - Pregnancy test for females of childbearing potential only

6.3. Posttreatment Assessments (\pm 5 days)

The posttreatment Weeks 4, 12, and 24 visits should be timed from the date of last administration of study drug for all subjects, regardless of whether they are a virologic failure or discontinued study drug early.

6.3.1. Posttreatment Week 4 (\pm 5 days)

The following procedures/assessments are to be completed for all subjects, 4 weeks after taking the last dose of study drug:

- Obtain vital signs (refer to Section 6.7.4)
- Assessment of AEs and concomitant medications
- Conduct pregnancy prevention counseling
- Obtain blood samples for tests:
 - Hematology
 - Chemistry
 - HCV RNA
 - HCV resistance sample
 - HBV DNA Sample
- Obtain urine sample for:
 - Pregnancy test for females of childbearing potential only (refer to Section 6.7.9)

6.3.2. Posttreatment Weeks 12 and 24 (\pm 5 days)

The following procedures/assessments are to be completed for all subjects, 12 and 24 weeks after taking the last dose of study drug:

- Obtain weight
- Obtain vital signs (refer to Section 6.7.4)
- Obtain blood samples for tests:
 - HCV RNA
 - HCV resistance sample

6.4. Assessments for Premature Discontinuation from Study

If a subject discontinues study dosing (for example, as a result of an AE), every attempt should be made to keep the subject in the study and continue to perform the required study-related follow-up and procedures (see Section 3.4, Stopping Rules and Discontinuation Criteria). If this is not possible or acceptable to the subject or investigator, the subject may be withdrawn from the study.

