3.4. Stopping Rules and Discontinuation Criteria

If a subject discontinues study dosing (for example, as a result of an adverse event [AE]), every attempt should be made to keep the subject in the study and continue to perform the required study-related follow-up procedures (see Section 6.3). If this is not possible or acceptable to the subject or investigator, the subject may be withdrawn from the study.

There is no option for SOF/VEL FDC dose reduction.

Subjects who permanently discontinue SOF/VEL FDC should complete an Early Termination (ET) visit. For subjects who have completed an ET visit, the posttreatment Weeks 4, 12, and 24 visits will be completed after the last dose of the study drug. When medically feasible, the medical monitor must be consulted prior to subject discontinuation.

Study drug must be discontinued in the following instances:

• Intercurrent illness that would, in the judgment of the investigator, affect assessments of clinical status to a significant degree. Following resolution of intercurrent illness, the subject may resume study dosing at the discretion of the investigator

- Unacceptable toxicity or toxicity that, in the judgment of the investigator, compromises the
 ability to continue study-specific procedures or is considered to not be in the subject's best
 interest
- Virologic failure (as defined in Section 3.4.2)
- Pregnancy of female subject (refer to Appendix 4)
- Significant protocol violation that impacts subject safety
- Subject request to discontinue for any reason; it is important to determine whether the withdrawal of consent is primarily due to an AE, lack of efficacy, or other reason
- Subject noncompliance
- Discontinuation of the study at the request of Gilead, regulatory agency or an Institutional Review Board (IRB)/Independent Ethics Committee (IEC)

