3.4.1. Toxicity-Based Stopping Criteria

The Medical Monitor must be consulted prior to dose discontinuation of SOF/VEL FDC unless the investigator believes that immediate action is warranted to ensure the continued safety of the subject.

Due to a clinical or laboratory event, administration of study drug may be discontinued. There is no option for SOF/VEL FDC dose reduction. If SOF/VEL FDC is stopped due to toxicity, it must not be restarted. In these cases that study drug is discontinued permanently, the subject must complete an ET visit. Posttreatment Week 4, 12, and 24 visits must also be scheduled, 4, 12, and 24 weeks from the last dose of study drug.

Subjects who meet any of the following laboratory criteria must stop all study drug:

- Elevation of ALT and/or AST above the upper limit of normal and > 5x Day 1 or nadir, confirmed by immediate repeat testing
- Abnormal elevation of ALT > 3 x Day 1 *and* total bilirubin > 2 x ULN, confirmed by immediate repeat testing
- Elevation of ALT > 15 x ULN, confirmed by immediate repeat testing
- Any Grade 3 or greater rash associated with constitutional symptoms
- Any Grade 4 adverse event or laboratory abnormality assessed (and confirmed by immediate repeat testing) as related to SOF/VEL FDC

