6.5. Early Termination (ET)

For subjects who have completed an ET visit, the posttreatment Weeks 4, 12, and 24 follow-up visits will be scheduled after the last dose of the study drug.

When medically feasible, the medical monitor must be consulted prior to subject discontinuation.

The following procedures/assessments are to be completed at an Early Termination visit:

- Perform complete physical examination (refer to Section 6.7.3)
- Obtain weight
- Obtain vital signs (refer to Section 6.7.4)
- Assessment of AEs and concomitant medications
- Perform 12-Lead ECG (refer to Section 6.7.5)
- Conduct pregnancy prevention counseling
- Assess adherence with study drug dosing regimen including pill count
- Collect any remaining study drug from the subject

- Obtain blood samples for tests:
 - Hematology
 - Chemistry
 - Coagulation tests
 - HCV RNA
 - HCV resistance samples
 - HBV DNA Sample
- Obtain urine sample for:
 - Pregnancy test for females of childbearing potential only

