3.5. Missing Data and Outliers

3.5.1. Missing Data

In general, missing data will not be imputed unless methods for handling missing data are specified. Exceptions are presented in this document.

For missing last dosing date of study drug, imputation rules are described in Section 3.7.1. The handling of missing or incomplete dates for AE onset is described in Section 7.1.5.2, and for prior and concomitant medications in Section 7.4.

For analyses of categorical HCV RNA data, missing posttreatment HCV RNA data will have the missing data imputed. Missing on-treatment HCV RNA will have missing data imputed up to the time of the last dose (for on-treatment displays). If the study day associated with the last dosing date of the study drug is greater than or equal to the lower bound of a visit window, and the value at the visit is missing, then the value will be imputed. If the study day associated with the last dosing date is less than the lower bound of a visit window, then the on-treatment value at that visit will remain missing.

If an HCV RNA data point is missing and is preceded and followed in time by values that are "< lower limit of quantification (LLOQ) target not detected (TND)," then the missing data point will be set to "< LLOQ TND." If a data point is missing and preceded and followed by values that are "< LLOQ detected," or preceded by "< LLOQ detected" and followed by "< LLOQ TND," or preceded by "< LLOQ TND" and followed by "< LLOQ detected," then the missing value will be set to "< LLOQ detected." In these situations, the data point will be termed a bracketed success; otherwise, the data point will be termed a bracketed failure (ie, \geq LLOQ detected). If a data point is missing and is not bracketed, the missing data point will also be termed a failure (ie, \geq LLOQ detected) except for SVR24, which will be imputed according to SVR12 status. Success for SVR12 who have no further HCV RNA measurements collected will be counted as a success for SVR24 due to the high correlation between these 2 endpoints.

For the analyses of continuous HCV RNA efficacy data, when and only when a missing HCV RNA value is imputed as < LLOQ TND or < LLOQ detected according to the imputation rule described above, the corresponding continuous value will be imputed to LLOQ – 1 IU/mL. No other imputation will be performed for continuous HCV RNA data.

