4. SUBJECT DISPOSITION

4.1. Subject Enrollment and Disposition

A summary of subject enrollment will be provided for each investigator. The summary will present the number and percentage of subjects in the Safety Analysis Set. For each column, the denominator for the percentage calculation will be the total number of subjects analyzed for that column.

A summary of subject disposition will be provided by HCV genotype (GT1, GT1 broken down [1a, 1b], GT2, GT2 broken down [GT2a/2c, GT2b]) and overall. This summary will present the number of subjects screened, the number of subjects enrolled, the number of subjects enrolled but never treated, and the number and percentage of subjects in each of the categories listed below

- In Safety Analysis Set
- In FAS
- Completed study treatment
- Did not complete study treatment with reasons for premature discontinuation of study treatment
- Completed study follow-up
- Did not complete the study follow-up with reasons for premature discontinuation of study follow-up

Among subjects who completed study treatment and who discontinued study treatment, the number and percentage of subjects will be summarized for:

- Who had no HCV posttreatment Week 4 assessment and thereafter (No HCV FU-4 Assessment and thereafter)
- Who had HCV posttreatment Week 4 assessment but no HCV posttreatment Week 12 and thereafter (With HCV FU-4 but No FU-12 and thereafter)

If a subject did not have any HCV RNA assessment \geq 21 days after the last dose of any study drug (ie, lower bound of FU-4 visit for HCV RNA data), the subject is categorized as having "No HCV FU-4 and thereafter." If a subject had the HCV FU-4 assessment but did not have any HCV RNA assessment \geq 70 days after the last dose of any study drug (ie, lower bound of FU-12 visit for HCV RNA data), the subject is categorized as having "With HCV FU-4 but No FU-12 and thereafter."

In addition, the total number of subjects who were enrolled, and the number of subjects in each of the disposition categories listed above will be depicted by a flowchart.

The following by-subject listings will be provided by subject identification (ID) number in ascending order to support the above summary tables:

- Disposition for subjects who complete study treatment and study follow up
- Disposition for subjects who did not complete study treatment and/or study follow up with reasons for premature discontinuation of study treatment and/or study
- Lot number and kit ID (if applicable)

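### A subject who stops study drug can be withdrawn from follow-up at the investigator's preference, which conflicts with the posttreatment visits required elsewhere and can turn an obtainable SVR12 result into an imputed failure

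*Protocol*

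**What the plan says.** Protocol 3.4 and 6.4 carry the same two-part rule for a subject who stops dosing. First, "every attempt should be made to keep the subject in the study". Then the exception: "If this is not possible or acceptable to the subject or investigator, the subject may be withdrawn from the study". No reason and no withdrawal of consent is required.

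Other sections have no such exception:

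- Protocol 6.3 times the Week 4, 12 and 24 visits from the last dose for all subjects, "regardless of whether they are a virologic failure or discontinued study drug early".
- Protocol 3.4.1, on toxicity stops: "Posttreatment Week 4, 12, and 24 visits must also be scheduled".
- Protocol 3.4.2 has subjects who stop for virologic failure complete the early termination (ET) visit and every posttreatment visit.

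On sampling, Protocol 3.4 says: "Subjects who permanently discontinue SOF/VEL FDC should complete an Early Termination (ET) visit". Protocol 6.5 lists what is done ("The following procedures/assessments are to be completed at an Early Termination visit"), and the list includes HCV RNA and a resistance sample. That visit is tied to stopping drug. Section 6.4, although titled as assessments for leaving the study, lists none.

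On analysis, the FAS keeps every treated subject (Protocol 8.2.1.1, SAP 3.1.2). SAP Table 2 accepts an HCV RNA as the FU-12 value from FU Day 70 to Day 146, and SAP 4.1 names Day 70 as the "lower bound of FU-12 visit for HCV RNA data". SAP 3.5.1 states: "If a data point is missing and is not bracketed, the missing data point will also be termed a failure", with an exception only for SVR24.

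**The concern.** SVR12 needs one blood sample taken long enough after the last dose, whether or not the course was completed. A subject who stopped early may still be cured, and follow-up involves no further study drug. A site can comply with the exception in 3.4 and 6.4 and, by doing so, defeat 3.4.1, 3.4.2 and 6.3. The withdrawn subject stays in the denominator. With no later sample the missing FU-12 value cannot be bracketed, so it counts as a failure. The sample size section states no allowance for missing results, and a trial of about 36 can absorb only two or three failures of any kind.

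**Working it through.** **Inputs.** n = 36, threshold 78%, expected SVR12 96%, two-sided exact binomial test at 0.05 (Protocol 8.5.1, 8.7.2; SAP 1.3). The documents give no withdrawal rate, so the number of forced failures, m, is an assumption.

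**1. The plan's own figure.** Neither document says how the two-sided exact p-value is formed, so both common definitions are shown.

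- Twice the smaller tail (agrees with Clopper-Pearson): 33/36 gives p = 2 × 0.0289 = 0.058; 34/36 gives p = 2 × 0.0080 = 0.016. Success needs 34/36. Power = P(X ≥ 34 | 36, 0.96) = 0.2516 + 0.3450 + 0.2300 = 0.8266.
- Summing point probabilities: 33/36 gives p = 0.045. Success needs 33/36. Power = P(X ≥ 33 | 36, 0.96) = 0.9454. The Clopper-Pearson lower limit at 33/36 is 77.5%, below the threshold.

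Both satisfy the stated power of more than 80%.

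**2. Effect of m forced failures.** The other 36 − m subjects each succeed with probability 0.96, so power = P(X ≥ r | 36 − m, 0.96).

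| m | r = 34 | r = 33 |
|---|---|---|
| 0 | 82.7% | 94.5% |
| 1 | 58.9% | 83.7% |
| 2 | 25.0% | 60.3% |
| 3 | 0% | 26.0% |

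**3. What observing the result recovers.** Suppose one such subject is sampled at Week 12, with chance q of SVR12. Under r = 34, power = q × P(X ≥ 33 | 35, 0.96) + (1 − q) × P(X ≥ 34 | 35, 0.96). This gives 71.3% for q = 0.5, 78.7% for q = 0.8 and 82.7% for q = 0.96, against 58.9% when imputed. The gain does not depend on assuming that early stoppers do as well as completers.

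**4. How often it could arise.** The clause covers only subjects who stopped dosing. Protocol 1.2.2 reports that all 102 subjects in one Japanese study completed treatment, and all but one of 117 in the other: 1/219. It also reports three discontinuations for adverse events in the second study, so 3/219 is shown as well. Let w be the stopping rate and suppose, as an extreme, that every stopper is withdrawn and set to failure. The success rate is then 0.96 × (1 − w).

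| w | P(at least 1 stop in 36) | P(2 or more) | Power, r = 34 | Power, r = 33 |
|---|---|---|---|---|
| 1/219 | 15% | 1.2% | 78.6% | 92.6% |
| 3/219 | 39% | 8.7% | 70.1% | 87.8% |

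At 1/219 the loss is 4.0 points (r = 34) or 2.0 points (r = 33). At 3/219 it is 12.6 or 6.8 points. At a given stopping rate the real loss would be smaller, because only some stoppers would be withdrawn at the investigator's preference while still willing to attend.

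**5. Which exits a sample could rescue.** The Week 12 visit falls on Day 84 ± 5, that is Days 79 to 89. A sample before Day 70 does not count as FU-12. A required exit sample would therefore recover SVR12 only for exits on about Days 70 to 78. For earlier exits only a later sample helps.

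**The case against.** The case for leaving the text alone has several sound parts.

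- Retention is the stated default, and 3.4 and 6.5 require consultation with the medical monitor before a subject is discontinued, when medically feasible. This stands and makes casual withdrawal less likely. It does not remove the investigator's ground for it.
- A reader might infer that the empty list in 6.4 causes the lost result. The documents do not support that. HCV RNA is already drawn at the ET visit, an exit sample before Day 70 leaves SVR12 a failure, and 6.6 allows an unscheduled sample at the investigator's discretion. An earlier exit sample could only help separate relapse from the category Other in SAP 6.2.2, because SAP 6.2.1 lets relapse rest on the last available posttreatment value.
- A reader might take 58.9% or 25.0% as the trial's likely power. They are conditional on one or two forced failures, and step 4 shows that early stopping is expected to be uncommon. A subject who stopped for virologic failure would rarely reach SVR12 anyway, so imputation seldom changes that result.
- Counting missing as failure works against a success claim. SAP 6.2.2 tabulates observed and imputed results with reasons, and SAP 4.1 counts subjects without FU-4 or FU-12 data. This stands: the handling is conservative and visible. Displaying a lost result does not recover it.
- A reader might also infer that safety follow-up simply ends. Protocol 7.3 asks for adverse events to be followed to resolution or stability if possible, and for relevant SAEs learned of later to be reported.

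**Conclusion.** The point holds in a limited form. Protocol 3.4 and 6.4 allow follow-up of a willing subject to end at the investigator's preference, and this is not reconciled with 3.4.1, 3.4.2 and 6.3. Where it happens with no HCV RNA at FU Day 70 or later, SVR12 becomes an avoidable imputed failure.

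One such case costs 23.8 points of power under a 34/36 rule (82.7 − 58.9) or 10.8 under 33/36 (94.5 − 83.7). The expected cost is probably only a few points, because stopping is rare and not every stopper would be withdrawn. The error rate for a success claim is not inflated.

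The figures assume exactly 36 treated subjects and a true rate of 96% in everyone not forced to failure. If that 96% already counts missing results as failures, the loss is overstated. The stopping rates come from populations and regimens that differ from this trial's (decompensated cirrhosis or prior DAA failure, some with ribavirin, some for 24 weeks).

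**What to change.** Low priority. Reconcile Protocol 3.4 and 6.4 with 3.4.1, 3.4.2 and 6.3:

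- State that stopping study drug and leaving the study are separate events.
- Remove investigator preference as a ground for ending follow-up, so that a subject leaves only on withdrawing consent or when follow-up is not possible. Striking the two words that name the investigator achieves only part of this, because the separate ground that follow-up is not possible stays in place. The new text should state both remaining grounds expressly.
- In 6.4, offer any subject who declines the full schedule a single HCV RNA with a resistance sample at posttreatment Week 12, or at exit if exit falls on or after FU Day 70.

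No rule on when drug is stopped changes, and the SAP windows and imputation rule can stay as they are. The cost is a short amendment and one blood sample in a few subjects.

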6.5. Early Termination (ET)

For subjects who have completed an ET visit, the posttreatment Weeks 4, 12, and 24 follow-up visits will be scheduled after the last dose of the study drug.

When medically feasible, the medical monitor must be consulted prior to subject discontinuation.

The following procedures/assessments are to be completed at an Early Termination visit:

- Perform complete physical examination (refer to Section 6.7.3)
- Obtain weight
- Obtain vital signs (refer to Section 6.7.4)
- Assessment of AEs and concomitant medications
- Perform 12-Lead ECG (refer to Section 6.7.5)
- Conduct pregnancy prevention counseling
- Assess adherence with study drug dosing regimen including pill count
- Collect any remaining study drug from the subject

- Obtain blood samples for tests:
 - Hematology
 - Chemistry
 - Coagulation tests
 - HCV RNA
 - HCV resistance samples
 - HBV DNA Sample
- Obtain urine sample for:
 - Pregnancy test for females of childbearing potential only

6.6. Unscheduled Visit

A subject should attend an unscheduled visit if requested by the sponsor or the investigator. The assessments are at the investigator's discretion as clinically indicated, but the investigator should, at a minimum, collect AE and concomitant medication information. At all unscheduled visits initiated for the purpose of confirming virologic failure, a HCV resistance sample must be collected.

6.7. Procedures and Specifications

6.7.1. Clinical Laboratory Analytes

Hematology: Hematocrit, Hemoglobin (Hb), Platelet count, Red blood cell count (RBC), White blood cell count (WBC) with differential (absolute and percentage) including Lymphocytes, Monocytes, Neutrophils, Eosinophils, and Basophils, Reticulocyte count and mean corpuscular volume (MCV).

Coagulation: INR, Prothrombin Activation %, Prothrombin time (PT), Activated partial thromboplastin time (aPTT)

Chemistry: Alanine aminotransferase (ALT/SGPT), Aspartate aminotransferase (AST/SGOT), Albumin, Alkaline phosphatase, Creatine Kinase, Creatinine, Direct Bilirubin, Total Bilirubin, Glucose, Lipase, Potassium, Sodium, phosphate, uric acid, FibroTest[®] (at Screening only)

Urinalysis: Blood, Glucose, Leukocyte esterase, pH, Protein, Urobilinogen. Reflex to microscopic urinalysis if dipstick result is abnormal.

Virological Tests: Serologies for HCV and HBV. HBV DNA (reflex testing done when ALT > 2x Day 1 value in subjects who are HBsAb or HBcAb positive at Screening). Serology and/or antigen testing for HIV, including reflex testing as necessary. HCV RNA will be measured using the COBAS[®] AmpliPrep/COBAS[®] TaqMan[®] HCV Quantitative Test,

version 2.0. HCV genotype and subtype will be determined using the Siemens VERSANT® HCV Genotype INNO-LiPA2.0 Assay. Gilead reserves the right to use alternate assays for HCV RNA and HCV genotype should the above assays become unavailable or are not definitive.

IL28B genotype will be determined by polymerase chain reaction (PCR) amplification of the SNP, rs12979860, with sequence specific forward and reverse primers and allele specific fluorescently labeled TaqMan® MGB probes. Gilead reserves the rights to use an alternate assay for IL28B determination should the above assay become unavailable.

Pregnancy Tests: Serum β-hCG or Urine β-hCG (if positive, requires immediate confirmation with Serum β-hCG), and serum FSH.

